10.3.3 Secondary outcome analysis

Qualitative methods will be used to analyse staff and participant interviews. These will include a phenomenological approach to the lived experience of the participants and stakeholders, through systematic thematic analysis of transcripts and interpretation of themes in the light of underpinning theory

10.4 Procedure(s) to account for missing or spurious data

Biosensor data will be reconciled with staff and patient reported data. Those that do not reconcile will be excluded.

10.5 Other statistical considerations.

N/A

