10 STATISTICS AND DATA ANALYSIS

10.1 Sample size calculation

This is a feasibility study and therefore recruitment target is not based on a sample size calculation, rather it is based on practical constraints and the length of the study.

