10.3.2 Primary outcome analysis

- Biosensor data analysed to determine whether or not an alarm would have been raised (and possibly the timing of the alarm)
- Staff measured outcomes reviewed to categorise whether there was cause for concern about the participant
- Above measures compared to determine either True Positive / False Positive / True Negative / True Positive events
- Sensitivity and Specificity are calculated for the complete data set (ideally with error bars calculated by an appropriate statistical method)

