11 DATA MANAGEMENT

11.1 Data collection tools and source document identification

Data will be collected via:

Case report form to collect participant demographics, any existing respiratory conditions, record potential SIRD events and outcomes and record issue/return of biosensor and tablet.

AIR Tool Questionnaire to assess participants' drug use behaviours. Completed once during the study.

Drug use diary to establish drug use, immediately prior to and during site stay. Completed at participants' discretion.

Satisfaction survey, completed at least once during the study.

Cloud data management for app respiratory data. The variability of normal respiratory patterns will be analysed using proprietary algorithms, facilitated by PneumoWave. This is fully anonymous.

Semi-structured interviews and focus group. Detailed in section 7.5 (Qualitative assessments)

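### The exclusion rule in section 10.4 does not exempt disagreements between alarm and staff outcome, so read literally it removes the false positives and false negatives the primary analysis must count

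*Protocol*

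**What the plan says.** Protocol section 10.3.2 builds the primary analysis from two sources. The index test is the retrospective alarm status: "Biosensor data analysed to determine whether or not an alarm would have been raised". The reference is the staff record: "Staff measured outcomes reviewed to categorise whether there was cause for concern about the participant". The two are then set against each other: "Above measures compared to determine either True Positive / False Positive / True Negative / True Positive events". (True Positive appears twice in that list and False Negative not at all; the second is presumably a slip for False Negative.) Finally, "Sensitivity and Specificity are calculated for the complete data set".

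Section 10.4, headed Procedure(s) to account for missing or spurious data, consists of two sentences: "Biosensor data will be reconciled with staff and patient reported data" and "Those that do not reconcile will be excluded". It does not say what counts as reconciling, who decides, or whether the decision is made without knowledge of the results.

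The participant-reported sources include a drug use diary, which section 11.1 describes as "Completed at participants' discretion". Section 10.3 leaves the SAP to be finalised before data lock; it was not at hand.

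**The concern.** A false positive is an alarm on a night when staff recorded no concern. A false negative is staff concern without an alarm. Each is a biosensor record that disagrees with the staff report, and section 10.4 names such disagreement, without qualification, as the ground for exclusion. Agreement between test and reference then serves both as the condition for entering the analysis and as the quantity being estimated.

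Section 2 says the data are to refine an alert algorithm and to separate overdose from substance use that does not end in overdose. The discordant records carry most of the information for that purpose. If they are removed, missed events and false alarms both disappear from the reported accuracy, and the case for the algorithm looks stronger than the data support. The protocol convenes no independent steering or data monitoring committee, so the wording itself has to prevent this.

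**Working it through.** The protocol states no expected sensitivity, specificity, event rate or number of observation periods, and in section 10.1 the "recruitment target is not based on a sample size calculation". There is therefore no figure of its own to reproduce. The inputs below are assumptions that show direction and range.

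**Step 1. Formula.** Let Se and Sp be the true values and f the share of discordant records excluded.

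- Observed sensitivity = Se / (Se + (1 − Se)(1 − f))
- Observed specificity = Sp / (Sp + (1 − Sp)(1 − f))

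Concordant records stay in and discordant ones leave only the denominator, so both values rise with f and cannot fall. Sensitivity depends only on the share of false negatives dropped, and specificity only on the share of false positives dropped. The two columns below can therefore be read separately if those shares differ.

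**Step 2. Assumed truth of 70% and 90%.**

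| Share of discordant records excluded | Sensitivity | Specificity |
|---|---|---|
| 0 | 0.70/1.00 = 70% | 0.90/1.00 = 90% |
| 0.5 | 0.70/(0.70 + 0.15) = 82% | 0.90/(0.90 + 0.05) = 95% |
| 0.8 | 0.70/(0.70 + 0.06) = 92% | 0.90/(0.90 + 0.02) = 98% |
| 1 | 0.70/0.70 = 100% | 0.90/0.90 = 100% |

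**Step 3. How many records this takes.** Assume 20 periods with staff concern and 980 without. False negatives number 20 × 0.30 = 6 and false positives 980 × 0.10 = 98. Full exclusion removes 6 + 98 = 104 of 1,000 records.

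**Step 4. Other assumed truths.**

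- 60% and 80%: half excluded gives 75% and 89%.
- 80% and 95%: half excluded gives 89% and 97%.
- 50% and 50% (an uninformative device): half excluded gives 67% and 67%, 90% excluded gives 91% and 91%, and full exclusion gives 100% and 100%.

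**Step 5. The linkage-only reading.** Suppose reconciling means only matching records to a person, a time and a wear period, and failure to match is unrelated to the result. All four cells then shrink by the same factor, which cancels. With 10% or 30% of records lost in this way, 70% and 90% stay at 70% and 90%.

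**The case against.** The strongest reply is that linkage was what the authors meant. The section heading concerns missing or spurious data. The protocol also collects what a linkage check needs: overnight staff checks that the device is worn and the app is running (section 4), and a case report form log of device issue and return (section 11.1). Section 10.3.2 lists false positives as a class to be counted, which a literal reading of section 10.4 would empty. This stands as a possible intention, and a reader should not infer that deletion of all errors is established. The reply does not rescue the text, which neither limits reconciling to linkage nor exempts discordant results.

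A second reply is that the SAP may define the term. It may. But section 10.4 states an exclusion rule outright. An SAP that applies it literally carries the bias forward, and one that departs from it needs the protocol sentence changed.

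Three stronger readings are tempting, and the document does not support them.

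- *Any algorithm, however poor, would look near-perfect.* This holds only when nearly all discordant records are dropped. With half dropped, the uninformative device in step 4 reaches only 67%.
- *Nights with a blank diary would be lost, and more often around an overdose.* Nothing says that a blank entry counts as failing to reconcile, and nothing in the protocol bears on when blanks occur. Section 7.4 allows the diary to be completed with staff support.
- *The rule flatly contradicts the reference in section 10.3.2 to the whole data set.* That phrase can mean pooled over all participants and nights after cleaning. The tension is real but does not settle the matter.

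**Conclusion.** The point holds as a defect in a stated rule. As written, section 10.4 permits the removal of the disagreements that section 10.3.2 exists to count, and read literally it requires it. The direction is certain on that reading: both measures move upwards only. The size is not known. It depends on the true accuracy and on the share excluded, neither of which the protocol gives. From an assumed 70% and 90%, the reported values would range from unchanged to 100% and 100%, with 82% and 95% if half of the discordant records go. The bias is nil if only linkage was meant and linkage failure is unrelated to the result.

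Feasibility status does not remove the problem, because sensitivity and specificity are the stated primary analysis. The sentence should be corrected before data lock.

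**What to change.** Replace the exclusion sentence in section 10.4 with text to this effect:

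> Reconciliation means matching biosensor records to study ID, date/time and wear period. Records are excluded only for pre-specified technical reasons (sensor not worn, no signal, timestamp or ID linkage failure), decided without knowledge of the alarm result or the staff outcome, and counted by reason. Disagreement between the alarm result and the staff-measured outcome is never a reason for exclusion; such records are classified as false positive or false negative against the staff-measured outcome. Disagreement with, or absence of, participant-reported data is not a reason for exclusion and does not change the classification.

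The last sentence keeps the reference standard as section 10.3.2 sets it, namely staff-measured outcomes alone. A diary entry of drug use without an alarm should not become a missed event.

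Report how many staff-recorded events fall among the excluded records, so that a reader can judge whether technical loss was related to outcome. An analysis that counts those events as missed is optional. It mixes adherence with algorithm accuracy and should be labelled as such. Correct the repeated True Positive in section 10.3.2 at the same time.

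The change is wording only and needs no new data collection. In practice, whoever decides exclusions needs an extract with the outcome fields left out, because site staff both check wear and record the outcome. The downside is that the accuracy figures may be less favourable.

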10.6 Economic evaluation

No economic evaluation will be performed.

11 DATA MANAGEMENT

11.1 Data collection tools and source document identification

Data will be collected via:

Case report form to collect participant demographics, any existing respiratory conditions, record potential SIRD events and outcomes and record issue/return of biosensor and tablet.

AIR Tool Questionnaire to assess participants' drug use behaviours. Completed once during the study.

Drug use diary to establish drug use, immediately prior to and during site stay. Completed at participants' discretion.

Satisfaction survey, completed at least once during the study.

Cloud data management for app respiratory data. The variability of normal respiratory patterns will be analysed using proprietary algorithms, facilitated by PneumoWave. This is fully anonymous.

Semi-structured interviews and focus group. Detailed in section 7.5 (Qualitative assessments)

11.2 Data handling and record keeping

The data management system will be an Excel spreadsheet. Password protected and stored on the University of Dundee server. No personal data will be held on the spreadsheet. This will be a pseudonymised data set, linked back to participants by unique study identifier and the enrolment log held at site. Data will be entered by a TCTU trial coordinator, transcribed from the CRFs, AIR tools and drug diaries collected from the participating sites. Data analysis will be carried out by King's College London (KCL). KCL will receive the entered pCRF data as a pseudonymised excel spreadsheet. Shared via encrypted email.

Interview and focus groups will be digitally recorded. All audio transfers will be conducted via audio recorder to a University (UoD or KCL) secured laptop. The interviews/focus group recordings will then be sent to KCL, who will complete a data sharing agreement with UoD. KCL will remove the audio file and related transcripts from their server within 30 days post transcription. Transcription will be completed by a research fellow at KCL. The transcriber will generate an anonymised transcript of the interview/ focus group recordings. Please note is not possible to safeguard against respondents compromising their anonymity or that of others during an interview/focus group, thus the need to anonymise during transcribing. No identifiable data such as interviewee names or interview locations and times will be attached to the audio file, i.e. all audio files will be labelled with an identifier number (which is only known and can only be linked to potentially identifiable information by the delegated researcher). These participant details including the identification number will be stored in a password protected digital file in University of Dundee/KCL, and only the delegated researcher will have access to this file. Participants will be assigned a unique study ID in order to protect their identity. The interview data will not be explicitly linked to specific clinical data for any participants.

Interview/focus group recordings will be deleted once the transcriptions have been received.

Interview/focus group transcripts will be stored on a secure University of Dundee/KCL device. They will be analysed and coded using thematic analysis. This process will be carried out by the research team. Thematic analysis will aid the identification of semantic meanings emerging from the interviews/focus groups, as well as allowing for interpretation of latent meanings. The analysis will help

understand the attitudes, feelings and perceptions of participants about the acceptability of wearing the device in the context of their daily lives and will allow identification of appropriate intervention strategies for the development of a clinical intervention pathway.

KCL will analyse the anonymised transcripts of the interviews and focus groups.

11.3 Access to Data

The CI, PIs and all institutions involved in the trial will permit trial related-monitoring, audits, REC review, and regulatory inspection. In the event of an audit, the CI and/or PI will allow the Sponsor, representatives of the Sponsor or regulatory authorities direct access to all trial records and source documentation.

11.4 Archiving

Archiving of study documents will be for ten years after the end of study.

12 MONITORING, AUDIT & INSPECTION

No formal monitoring is planned. The trial coordinator will be in regular contact with sites to ensure trial procedures are being followed correctly and participant safety and data integrity safeguards are in place.

13 ETHICAL AND REGULATORY CONSIDERATIONS

13.1 Research Ethics Committee (REC) review& reports

The study will be conducted in accordance with the principles of good clinical practice (GCP). In addition to Sponsorship approval, a favourable ethical opinion will be obtained from the appropriate REC(s) will be obtained prior to commencement of the study.

13.2 Public and Patient Involvement

People with lived experience of injecting drug use have been consulted about this study and have been involved in focus groups discussing the PneumoWave technology platform.

13.4 Regulatory Compliance

Before any site can enrol participants into the trial, the CI, PI or delegate will ensure that appropriate approvals from participating organisations are in place.

For any amendment to the trial, the CI, PI or delegate, in agreement with the sponsor, will submit information to the appropriate body in order for them to issue approval for the amendment. The CI, PI or delegate will work with sites so they can put the necessary approvals and arrangements in place to implement the amendment to confirm their support for the trial as amended.

13.5 Protocol compliance

Prospective, planned deviations or waivers to the protocol are not allowed, e.g. it is not acceptable to enrol a participant if they do not meet the eligibility criteria or restrictions specified in the trial protocol. Trial staff will not implement deviations to the protocol except where necessary to eliminate an immediate hazard to trial participants.

Accidental protocol breaches can happen at any time. They will be adequately documented on the relevant forms and reported to the CI and Sponsor using the TASC Breach Reporting and Corrective Actions/Preventative Actions Form. If there is a breach of the protocol, the nature of and reasons for the breach will be recorded in the TMF and documented in the trial Breach Report Log. Breaches from the protocol which are found to frequently recur are not acceptable, will require immediate action and could potentially be classified as a serious breach.

13.6 Notification of Serious Breaches to GCP and/or the protocol

A “serious breach” is a breach which is likely to effect to a significant degree –

- a) the safety or physical or mental integrity of the participants of the trial; or
- b) the scientific value of the trial

The sponsor will be notified immediately of any case where the above definition applies during the trial conduct phase. The sponsor of a clinical trial will notify the licensing authority in writing of any serious breach of

- a) the conditions and principles of GCP in connection with that trial; or
- b) the protocol relating to that trial, as amended from time to time.

If a serious breach of the protocol or GCP is suspected, this will be reported to the Sponsor immediately using the Breach Reporting & Corrective Actions/Preventative Actions Form and will be recorded in the CRF and documented in the study Breach Report Log.

If a breach necessitates a subsequent protocol amendment, this will be submitted as per section 13.10.

13.7 Data protection and patient confidentiality

The CI and trial staff will comply with the requirements of the General Data Protection Regulation (EU) 2016/679 (GDPR) and the UK Data Protection Act 2018 or any subsequent amendment or replacement thereof with regard to the collection, storage, processing and disclosure of personal data and will uphold the principles of GDPR in Article 5.

While there is no NHS involvement in the study, the CI and trial staff will adhere to the NHS Scotland Code of Practice on Protecting Participant Confidentiality or local equivalent.

All trial records and data will be managed in a manner designed to maintain participant confidentiality. All records, electronic or paper, will be kept in a secure storage area with access limited to appropriate trial staff only. Computers used to collate data will have limited access measures via usernames and passwords. Age and gender will be the only personal identifiable details held on the Excel data management system.

Personal data or data concerning health will not be released without the existence of a legal basis for processing under Articles 6 and 9 of GDPR, such as official authority 6(1)e or substantial public interest 9(2)g. The CI and trial staff will not disclose or use for any purpose other than performance of the trial, any data, record, or other unpublished, confidential information disclosed to those individuals for the purpose of the trial. Prior written agreement from the Sponsor will be required for the disclosure of any said confidential information to other parties.

Access to collated participant data will be restricted to the CI and appropriate delegated trial staff. PneumoWave will not have access to personal identifiable details.

Published results will not contain any personal data that could allow identification of individual participants.

13.8 Financial and other competing interests for the chief investigator, PIs at each site and committee members for the overall trial management

Not applicable.

13.9 Indemnity

The University of Dundee are Sponsoring the trial.

Insurance. – The University of Dundee holds Clinical Trials indemnity cover which covers the University's legal liability for harm caused to participant

Indemnity. The Sponsor does not provide trial participants with indemnity in relation to participation in the Trial but have insurance for legal liability as described above.

13.10 Amendments

Amendments to the protocol will be conducted in compliance with Sponsor Standard Operating Procedures. The decision to amend the protocol will lie with the CI after consultation with the TMG and trial statistician. The CI will seek Sponsor approval for any amendments to the Protocol or other approved trial documents. The Sponsor will decide whether an amendment is substantial or non-substantial. The CI will be responsible for submitting the amendment to the appropriate regulatory authorities and communicating amendments to sites. Amendments to the protocol or other trial documents will not be implemented without approval from the Sponsor and subsequent approval from the appropriate REC and/or CA, as appropriate, and appropriate site approvals. The amendment history will be detailed in an Amendment Log.

13.11 Access to the final trial dataset

The CI and Trial Statistician will have access to the final trial dataset. Access to the final trial dataset to others will be approved by the CI.

14 DISSEMINATION POLICY

14.1 Dissemination policy

Ownership of the data arising from this study resides with the study team and the University of Dundee. On completion of the study, the study data will be analysed and tabulated, and a clinical study report will be prepared.

The clinical study report will be used for publication and presentation at scientific meetings. Investigators have the right to publish orally or in writing the results of the study.

Summaries of results will also be made available to Investigators for dissemination within their clinical areas (where appropriate and according to their discretion).

The results of the study will be disseminated to participants' who remain living in the supported accommodation at the time of publication. Results will be disseminated in the form of a newsletter, provided by the study team to the supported accommodation.

16. APPENDICES

16.1 Appendix 1 – Schedule of Procedures

Procedures	Baseline	Ongoing until end of study	End of study
Informed consent	X		
Demographics	X		
Respiratory medical history	X		
Eligibility assessment	X		
AIR Tool ^a	*	*	*
Fit device and issue tablet	X	X	
Satisfaction Survey ^b		X	
Adverse Events		X	
Drug Use Diary		X	
Interview ^c			X
Focus Group ^c			X

^a = completed once during the study

^b = completed at least once, but can be completed multiple times

^c = sub-section of participants
